6 STUDY PROCEDURES

6.1 Schedule of Evaluations Participant Name: _____ Mention DATES mm/dd/yy in below table for each activity.

Assessment	Screening: Visit 1 (Day 0)	Baseline, Enrollment, Randomization: Visit 1 (Day 0)	Treatment Visit 2 Day 7 (± 2 Days)	Treatment Visit 3 Day 14 (± 2 Days)	Treatment Visit 4 Day 21 (± 2 Days)	Treatment Visit 5 Day 28 (± 2 Days)	Treatment Visit 6 Day 35 (± 2 Days)	Follow up 7 Day 42 (± 2 Days)	Follow-up: Final Visit Day 132 (± 2 Days)
Informed Consent Form	X								
Screening tool	X								
Inclusion/Exclusion Criteria	X								
Demographics		X						X	X
Blood pressure		X						X	X
Bodyweight & height		X						X	X
Waist circumference		X						X	X
Hair samples		X							X
Stress		X						X	X
Anxiety & Depression		X						X	X
Coping Strategies		X						X	X
Self-efficacy		X						X	X
Family Conflict Resolution		X						X	X
Family Satisfaction		X							
Enrollment/Randomization		X							
Intervention Session and its assessment using fidelity form			X	X	X	X	X	X	X
Adverse Events		X	X	X	X	X	X	X	X

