1 STUDY OBJECTIVES

1.1 Hypothesis: Immigrants in the Problem Management Plus for Immigrants (PMP-I) will have significantly lower stress and anxiety/depressive symptoms than immigrants in the talk program with Community Support Service pamphlets (CSS).

1.2 Objective: The current study aims to pilot test the feasibility and acceptability of PMP-I among Bhutanese immigrants 18 years and older living in Massachusetts.

Aim 1: Adapt and culturally modify PMP to develop PMP-I as a family-based preventative intervention.

- a) Develop a training guide and intervention curriculum;
- b) Obtain iterative feedback about the format, ease of use, and implementation barriers from participants, facilitators, and community members.

Aim 2: Test the feasibility, acceptability, and preliminary outcomes of PMP-I with trained community facilitators.

- a) Assess i) recruitment, session attendance, and retention rates and program acceptability using checklists from participants; ii) feasibility of measures for assessing inclusion/exclusion, the fidelity of intervention delivery, mediators of response, and outcomes using checklists from facilitators; and iii) barriers and facilitators of intervention using interview and focus group discussion with participants and facilitators.
- b) Test preliminary effects of PMP-I vs. talk program with community support services pamphlets (CSS) using a small randomized pilot trial (N=116 families; 58 families per intervention and control), on perceived stress, anxiety and depressive symptoms (primary), physiological stress assessed in hair cortisol (secondary), and self-efficacy and coping strategy, family wellbeing, and social networking (targets), with assessments at baseline, post-intervention, and 3-month post-intervention.
- c) Evaluate the relationships between targets and outcomes and explore mediators (e.g., coping) of intervention-outcome relation.

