Figure 1 provides a visual representation of our proposed analyses, in which treatment is a predictor of treatment targets or mechanisms (i.e. the mediators such as coping), which are in turn associated with outcomes. As reviewers 1 and 3 note, in mediational analyses, variables must be measured in *temporal sequence*.

Figure 2 provides a visual representation of our proposed temporal sequence of variable measurement for mediational analyses, in which treatment randomization occurs before mediator target measurement, which in turn are collected before the outcome measure used in the proposed analyses. Second, it is crucial to test the *indirect effect* (a*b paths) of the treatment on the outcome through the hypothesized mediators. As the indirect

effect is not normally distributed, we will assess its significance via Monte Carlo simulated confidence intervals, which are the recommended counterpart in multilevel mediation to bootstrapped confidence intervals used in single-level analyses.⁶⁶⁻⁶⁸

Each potential mediational sequence will be tested in this manner (see **Table 1** for mediators and outcomes to be tested). While we acknowledge that mediational analyses are difficult to adequately power in a sample of our proposed size,⁶⁷ we believe these preliminary analyses will help identify potential mechanisms for our treatment effect. If baseline differences in treatment groups are found in either the mediating or outcome variables, baseline measures will be controlled for in all analyses. Sample mixed-format multilevel equations are provided below, where the nesting of measures (i) within families (j) is accounted for by the random effects u_{0js} : γ_{01} in the Mediator equation is the ‘a path’, and γ_{10} in the Outcome equation is the ‘b path.’

Table 1 Mediators and Outcome Variables

Mediators (Targets)	Outcomes
Coping, Self-Efficacy	Perceived Stress
Family or Social Support	Physiological Stress
Family Conflict Resolution	Anxiety Symptoms
Family Satisfaction	Depressive Symptoms
Family or Social Network	

$$T2Mediator_{ij} = \gamma_{00_Med} + \gamma_{01_Med} * TreatmentCondition_j + u_{0j_Med} + r_{ij_Med}$$

$$T3Outcome_{ij} = \gamma_{00_Out} + \gamma_{10_Out} * T2Mediator_{ij} + \gamma_{01_Out} * TreatmentCondition_j + u_{0j_Out} + r_{ij_Out}$$

The key estimates are the association of the treatment condition with the mediator (γ_{01_Med} , a path) and the association of the T2 mediator with the T3 Outcome (γ_{10_Out} , b path).

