10 DATA COLLECTION AND QUALITY ASSURANCE

10.1 Data Collection Forms

10.1.1 Survey Questionnaire: Trained community research assistants will collect information from participants using attached screening and survey questionnaires and instruction sheets to measure blood pressure, body weight, height, and waist circumferences, and hair samples collection. PI will provide two full days of training to RAs on all aspects of the study procedure, including recruitment procedure, informed consent, screening, pre, and post-assessment survey tools using a questionnaire, anthropometric and blood pressure measurement, hair sample collection and storage procedure, logistics materials, and administrative details. Training sessions include document review, role-play, and practice exercises. We plan to recruit the RAs who worked in our pilot studies to conduct surveys, measure anthropometric parameters and blood pressure, and collect hair samples. The quality of their data collection was excellent in our previous baseline and pilot intervention studies. RAs will complete required human subject research training, including the Collaborative Institutional Training Initiative (CITI) and Good Clinical Practice (GCP).

10.1.2 Screening tool: Trained RAs will use the Patient Health Questionnaire (PHQ-9), a screening questionnaire for depression, to screen the study participants and record each screened participant in the screening log.

10.1.3 Survey questionnaire: Trained RAs will use the survey questionnaire, including various validated scales to measure stress, anxiety and depressive symptoms, coping, social support, social networking, family conflict resolution, and family satisfaction to collect information from the participants at baseline, post-intervention, and 3-month post-intervention. These tools have high internal consistency among the Bhutanese population in our pilot studies (Cronbach's alpha range 0.78 – 0.94).³⁹

10.1.4 Body measures: Trained RAs will follow standard procedures mentioned in the “Training Manual for Research Assistant” to measure blood pressure, body weight, height, and waist circumferences of study participants.

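### The section 6.1 schedule contradicts section 10.1.3, Aim 2b and Table 1 on when family satisfaction, social support and social network are measured; followed alone, it leaves three of five mediator rows without T2 data

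*Combined protocol and SAP*

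**What the plan says.** **Section 6.1 (schedule).** Stress, anxiety and depression, coping, self-efficacy and "Family Conflict Resolution" are each marked at baseline, Day 42 and Day 132. The next row, "Family Satisfaction", is marked at baseline only. Social support and social network have no row, although section 6.2.2 defines an instrument for each.

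**Section 10.1.3.** The survey questionnaire measures "coping, social support, social networking, family conflict resolution, and family satisfaction to collect information from the participants at baseline, post-intervention, and 3-month post-intervention".

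**Aim 2b (section 1.2).** The targets are "self-efficacy and coping strategy, family wellbeing, and social networking (targets), with assessments at baseline, post-intervention, and 3-month post-intervention".

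**Section 9.2, Aim 2c.** Table 1 lists five mediator rows. They include "Family or Social Support", family satisfaction and "Family or Social Network". The b path is "the association of the T2 mediator with the T3 Outcome", and the text adds: "Each potential mediational sequence will be tested in this manner".

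**The concern.** The mediation model uses a mediator measured after randomisation and before the outcome. A mediator recorded only at baseline, or not at all, cannot enter it. Section 6.1 gives that pattern for three of the five Table 1 rows, while section 10.1.3 gives full collection for the same three. The plan therefore does not settle whether the data needed for a large part of Aim 2c will exist.

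The schedule matters in practice for two reasons. It is the only place that sets out, instrument by instrument, what is done at each visit. It also carries a participant-name line and an instruction to enter dates, so it serves as a completion form for each participant. A form with no cell for a scale cannot show that the scale was missed, and a Day 42 score that was not taken cannot be recovered later.

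**Working it through.** The plan states no figure to reproduce here. The check sets the sections side by side and then counts.

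**Step 1. When is T2?** Section 9.2 says that randomisation comes before the mediator measurement, which in turn comes before the outcome. Section 4.3 places allocation after the baseline survey, so baseline is too early. Day 132 is the last assessment (section 6.2.4), so it must carry the T3 outcome. Hair cortisol, one of the Table 1 outcomes, is scheduled only at baseline and Day 132, which agrees. Day 42 is the only outcome assessment between the two, so T2 is Day 42.

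**Step 2. Each Table 1 mediator row against the three sources**

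| Table 1 row | 6.1 baseline | 6.1 Day 42 | 6.1 Day 132 | 10.1.3, all three times | Aim 2b, all three times |
|---|---|---|---|---|---|
| Coping, self-efficacy | yes | yes | yes | coping named; self-efficacy not named | both named |
| Family or social support | no row | no row | no row | social support named | not named |
| Family conflict resolution | yes | yes | yes | named | within family wellbeing |
| Family satisfaction | yes | blank | blank | named | within family wellbeing, if read broadly |
| Family or social network | no row | no row | no row | social networking named | named |

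**Step 3. Rows with no T2 value**

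- Schedule alone: 3 of 5 (support, satisfaction, network).
- Section 10.1.3: 0 of these 3.

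**Step 4. Mediator-outcome pairs.** Table 1 lists four outcomes: perceived stress, physiological stress, anxiety symptoms and depressive symptoms.

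- Counting Table 1 rows: 5 × 4 = 20 pairs, of which 3 × 4 = 12 are affected (12/20 = 60%).
- Counting coping and self-efficacy as two mediators: 6 × 4 = 24 pairs, of which 12 are affected (12/24 = 50%).
- Under section 10.1.3: 0 affected on either count.

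**Step 5. Can the model cope with an absent mediator?** Maximum likelihood can use incomplete records when some participants have the mediator. If nobody has it at T2, the first Aim 2c equation has no response variable and the second has no mediator term. Neither the a path nor the b path can be estimated.

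**The case against.** The strongest case on the other side is that the plan does provide for these measurements. Section 10.1.3 states the timing outright and says that the research assistants work from a survey questionnaire containing these scales. The questionnaire itself is an attachment that is not among the documents, so an omission at Day 42 cannot be demonstrated. This stands. A reader might infer from section 6.1 that the three mediators will have no T2 data, or that baseline-only collection of family satisfaction was a deliberate choice. The documents support neither. Section 10.1.3 contradicts the first, and nothing in the text gives a reason for the second.

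Two further points stand. The total of 20 pairs appears nowhere in the plan and depends on counting Table 1 rows. Aim 2c is also exploratory, and section 9.2 concedes that mediation is hard to power at this sample size.

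The objection does not remove the contradiction. Sections 6.2.3 and 6.2.4 describe the Day 42 and Day 132 visits only as assessments of study outcomes, without naming instruments, and section 6.2.2 describes the scales under the baseline assessments. Neither decides between sections 6.1 and 10.1.3. Aim 2b is clear for social networking, covers family satisfaction only if family wellbeing is read to include it, and does not mention social support. Loss of a row or mark in text extraction cannot be excluded, but it is unlikely. The neighbouring rows read cleanly, and the blank Day 42 cell for hair samples matches the time frame in section 3.

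**Conclusion.** The concern holds as an internal contradiction with a conditional consequence. Section 6.1 disagrees with section 10.1.3, with Aim 2b in part, and with what Table 1 requires. If the schedule is followed, three of the five mediator rows have no T2 value and their mediation models cannot be estimated, which affects 12 of 20 pairs, or 12 of 24 on the finer count. If section 10.1.3 is followed, nothing is lost.

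The conclusion assumes that T2 is Day 42. This follows from the stated sequence, but the figure showing that sequence is not available. It also assumes that the extracted schedule is complete. Every primary and secondary outcome has its own schedule row, so the main comparison is untouched. The correction should be made, because the loss would be irrecoverable and the change is small, but the main analysis does not depend on it.

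**What to change.** Reconcile section 6.1 with section 10.1.3:

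- Add a Social Support row (MSPSS) and a Social Network row, each marked at baseline, Day 42 and Day 132.
- Add marks for Family Satisfaction at Day 42 and Day 132.
- If any of these is not meant to be collected after baseline, remove it from Table 1 and correct section 10.1.3 and, where relevant, Aim 2b.

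As a side note, name self-efficacy in the section 10.1.3 list for consistency. Its collection is not in doubt, because section 6.1 marks it at all three assessments and Aim 2b names it.

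The cost is a corrected table and the matching text edits. There is no participant burden beyond what section 10.1.3 already commits to.

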6.2 Description of Evaluations

6.2.1 Screening Evaluation

These evaluations occur to determine if the participant is eligible for the study.

Consenting Procedure

Trained RAs will meet interested participants and inform them about screening and study procedures to each participant using UMass Amherst IRB-approved single informed consent form. A copy of the informed consent form will be provided to each participant for their review. If they want, RAs can read informed consent for them. Participants will be given enough time to review informed consent and ask questions if they have any confusion. RAs will ensure that participants understand screening, study procedure, privacy and confidentiality of private information, and NDA data sharing policy. They will be reminded that their participation in the study is voluntary and free to leave the study without penalty. Once participants understand about study details, RAs will request them to do their signature or write their initials or fingerprint for those who cannot write their names in the two copies of the informed consent form before collecting their information. One copy of the signed informed consent form will be provided to each participant. We will not recruit any individuals who are unable to consent for themselves. The signed informed consent form will be stored securely in the locked cabinet of the PI's office. (Please find attached informed consent for details)

Screening

RAs will screen interested participants after obtaining their informed consent on the same day. We plan to include eligible Bhutanese adults aged 18 or older interested in participating in the study as primary study participants. This includes parents and their adult children aged 18 and above. At baseline, we will use our screening tool to identify individuals without significant depressive symptoms, as we aim to evaluate the effect of our intervention to prevent depression rather than treat depression. Eligibility criteria for our primary study participants include Bhutanese adults 18 years or older (both parents and children of each family) resettled in Massachusetts with a score of 14 or below on the Patient Health Questionnaire (PHQ-9), a screening

questionnaire for depression. Our statistical analysis will focus on data from primary study participants only with baseline PHQ-9 scores 14 or below. However, all other interested adult family members, both parents and their adult children, regardless of PHQ-9 score, will be invited to participate in our study, to maintain the confidentiality of each family member's mental health status within their family.

Besides, individuals with PHQ-9 screening scores '15-19' (moderately severe depression) and '20-27' (severe depression) will be provided with feedback on their screening questionnaire outcomes confidentially and encouraged to consult their primary health care providers. A field supervisor can provide the necessary support for setting up an appointment with primary health care providers and emergency services, as needed. A field supervisor also will make a follow-up home visit to monitor their mental health condition, as necessary. Participants with clinically diagnosed mental disorders and those taking psychiatric medications for any mental health problems will also be encouraged to participate in the family-based intervention activities. However, we will not consider data from those participants with PHQ-9 scores of 15 or above or diagnosed with mental health problems in our primary statistical analysis. RAs will keep a record of participants using the attached screening log.

SCREEN LOG

Study: _____

Site: _____

Investigator: _____

Screening Number	Participant Names	Date of Birth	Gender	Screening Date	Screening Status (use codes below)	Consent Obtained	Enrolled (if no, indicate reason from codes below)	Date Enrolled
  		/ / mm/dd/yyyy	 M  F	/ / mm/dd/yyyy		 Yes  No	 Yes  No	/ / mm/dd/yyyy
  		/ / mm/dd/yyyy	 M  F	/ / mm/dd/yyyy		 Yes  No	 Yes  No	/ / mm/dd/yyyy
  		/ / mm/dd/yyyy	 M  F	/ / mm/dd/yyyy		 Yes  No	 Yes  No	/ / mm/dd/yyyy
  		/ / mm/dd/yyyy	 M  F	/ / mm/dd/yyyy		 Yes  No	 Yes  No	/ / mm/dd/yyyy
  		/ / mm/dd/yyyy	 M  F	/ / mm/dd/yyyy		 Yes  No	 Yes  No	/ / mm/dd/yyyy

Sample Screen Status Codes:

- 1-Eligible
- 2-Eligible, declined participation
- 3-Not Eligible
- 4-Eligible, lost to follow up
- 5-Other, specify in space provided

6.2.2 Enrollment, Baseline, and Randomization

Enrollment

In this study, the enrollment date is the day the participant has met all the screening criteria and signs a single informed consent form that describes both screening and study procedures. RAs will record the enrollment date on a case report form along with the allowable window between screening and randomization.

Baseline Assessments

For participants who will have successfully been screened for eligibility and are enrolled in the study, baseline assessments will be performed to measure the study outcome on the same day of enrollment. We will measure study outcomes as listed below:

Anxiety and Depressive Symptoms

The Hopkins Symptom Checklist-25 (HSCL-25)² will be used to measure anxiety and depressive symptoms² experienced over the past month. It is composed of a 10-item subscale for anxiety and a 15-item subscale for depression, with each item scored on a Likert scale from 1 (not at all) to 4 (extremely). The scale was validated for use in Nepal with a clinical DSM-IV diagnosis of major depressive disorder. The sensitivity and specificity with a cutoff point of 1.75 were 0.87 and 0.60, respectively, with an area under the curve of 0.79.⁵⁰ The HSCL-25 has widely been used in studies among refugees in other countries as well as Nepal. The HSCL-25 score was categorized into two groups: the cutoff score of 1.75, depressed (1.75 or more), and not depressed (below 1.75). The scale has high internal consistency for anxiety (Cronbach's $\alpha = 0.92$) and depression (Cronbach's $\alpha = 0.94$) in our previous Bhutanese study.³⁹

Perceived Stress

The 10-item Cohen Perceived Stress Scale (PSS)¹ will be used to assess perceived stress. The PSS uses a 5-point Likert scale (ranging from 0, “never” to 4, “very often”) to assess psychological stress experienced during the past month, including

the extent to which situations felt unpredictable, uncomfortable, and overwhelming. The items included in the PSS scale are easy to understand as it was designed for use with community samples with junior high school education. This scale has been widely used in different populations, including immigrants. The scale has high internal consistency (Cronbach's $\alpha = 0.80$) in our previous Bhutanese study.³⁹ Items were summed to provide a total score with higher scores indicating greater perceived stress.

Physiological stress

We will use the ELISA cortisol hair-test (average hormone levels over the past three months) as a biomarker to measure physiological stress. Neuroendocrine indicators, such as cortisol, are effective stress biomarkers because they are the first to respond to a given stressor and coordinate the physiological response of other bio-physiological systems. Biomarker measurement helps overcome the limitations of self-report because it provides an objective marker of stress levels. Hair samples will be processed in the neuroendocrine lab at UMass.^{51, 52} Sensitive and specific enzyme immunoassay (Salmetrics) will be used for the analysis. The assay has intra- and inter-assay coefficients of variation of <10%. The cortisol distribution will be tested for normality, and if the data are not normal, they will be log-transformed before statistical analysis.

Coping strategy

Coping strategy⁵⁴ will be measured using a 32-item Coping Strategies Inventory-Short Form (CSI-SF). The CSI-SF includes two overall coping factors, Engagement and Disengagement, and four secondary factors, Problem Engagement, Problem Disengagement, Emotion Engagement, and Emotion Disengagement. The CSI-SF scale (Cronbach's $\alpha = 0.95$) and its subscales problem engagement (Cronbach's $\alpha = 0.87$), emotion engagement (Cronbach's $\alpha = 0.89$), problem disengagement (Cronbach's $\alpha = 0.81$), and emotion disengagement (Cronbach's $\alpha = 0.78$) have high internal consistencies in our previous Bhutanese study.³⁹ A sample item for this scale is, "I worked on solving the problems in the situation." Participants were asked to rate

their responses on a 5-point Likert-type scale ranging from *not at all (1)* to *very much (5)*. Items are summed to provide sub-scale and larger composite scores with higher scores associated with greater adherence to that coping style.

Self-efficacy

Self-efficacy will be measured using a 26-item Coping Self-efficacy(CSE)⁵⁵ scale for coping with challenges and threats. A sample item for this scale is “Do something positive for yourself when you are feeling discouraged.” Each item of the scale will be rated on an 11-point scale Likert-type scale ranging from *(0) cannot do at all, (5) moderately certain can do, and (10) certain can do*. Graded items will be summed up to provide a total score, and higher scores indicate high self-efficacy. The scale has high internal consistency (Cronbach’s $\alpha = 0.96$) in our previous Bhutanese study.³⁹

Social support

Perceived social support will be measured using a 12-item Multidimensional Scale of Perceived Social Support (MSPSS)^{56, 57} including support from friends, family, and significant others, and has been used cross-culturally. A sample item for this scale is, “My family tries to help me.” Each item of the scale will be rated on a 5-point Likert-type scale ranging from *strongly disagree (1)* to *strongly agree (5)*. Graded items will be summed up to provide a total score, and higher scores indicate high social support. The scale has high internal consistency (Cronbach’s $\alpha = 0.92$) in our previous Bhutanese study.³⁹

Social network

A social network including size, closeness, and frequency of active and intimate networks of family or friends will be measured using a 12-item version of the “Lubben Social Network” scale.⁵⁸ It consists of six questions, which assess kinship ties, and a comparable set of six questions, which determine friend ties by replacing the word relatives with the word friends. A sample item from this scale is, “How often is one of your relatives available for you to talk when you have an important decision to make?” Participants will be asked to respond on a 6-point Likert-type

scale, ranging from *less social engagement (0)* to *more social engagement (5)*. Scores across all items will be summed up to provide a total score, and higher scores indicate a high social network. We prepared three questions to measure cross-cultural social ties following a similar pattern. The scale has high internal consistency for kinship ties (Cronbach's $\alpha = 0.78$), friendship ties (Cronbach's $\alpha = 0.80$), and cross-cultural social ties (Cronbach's $\alpha = 0.74$) in our previous Bhutanese study.³⁹

Family conflict resolution

Family conflict resolution, including positive or negative resolution, effective communication, and discussion of differences will be measured using a 17-item version of the “Family Conflict Resolution” scale.⁵⁹ A sample item from this scale is, “In my family, when we have an argument we usually work it out.” Participants will be asked to respond on a 7-point Likert-type scale, ranging from *never (1)* to *always (7)*. Scores across all items will be summed up to provide a total score, and higher scores indicate high family well-being. The scale has high internal consistency (Cronbach's $\alpha = 0.92$) in our previous Bhutanese study.³⁹

Family satisfaction: Family satisfaction with various aspects of family functioning, including family closeness, flexibility, and communication will be measured using a 10-item family satisfaction scale.⁶⁰ A sample item from this scale is, “How satisfied are you with the degree of closeness between your family members.” Participants will be asked to respond on a 5-point Likert-type scale, ranging from *very dissatisfied (1)* to *extremely satisfied (5)*.

Randomization

Participants will be randomly assigned to intervention and control groups within 7-days of baseline survey completion. The first session of intervention will be delivered to the intervention and control groups within the seven days of baseline survey completion.

